2. STUDY OBJECTIVES

2.1. Primary Objective

The primary objective of this study is to evaluate the safety and efficacy of pitolisant compared with placebo in treating EDS in patients with PWS ages 6 to 65 years.

2.2. Secondary Objectives

2.2.1. Key Secondary Objectives

The key secondary objectives of this study are to evaluate caregiver-rated impressions of severity of EDS and clinician-rated impressions of severity of overall clinical status in patients with PWS ages 6 to 65 years treated with pitolisant compared with placebo.

2.2.2. Other Secondary Objectives

Other secondary objectives of this study are to evaluate the following in patients with PWS ages 6 to 65 years:

- The impact of pitolisant on behavioral symptoms
- The impact of pitolisant on cognitive functions
- Change in caregiver burden
- Effectiveness of pitolisant during long-term treatment

2.3. Exploratory Objectives

The exploratory objectives of this study are to evaluate the following in patients with PWS ages 6 to 65 years:

- The impact of pitolisant on hyperphagia
- The impact of pitolisant on ghrelin levels
- The PK of pitolisant and its major metabolite, BP1.3484
- The relationship between levels of pitolisant (PK) and treatment effect (pharmacodynamics)

3. INVESTIGATIONAL PLAN AND ENDPOINTS

3.1. Description of the Study Design

3.1.1. Overall Study Design

This is a randomized, double-blind, placebo-controlled, parallel group, Phase 2 POC study in patients (ages 6 to 65 years) with PWS, followed by an optional OLE Phase.

The study will consist of a Screening Period (up to a maximum of 45 days), an 11-week Double-Blind Treatment Phase (including a Titration Period and an 8-week Stable Dose Period), and an optional OLE Phase. The OLE Phase will be multi-year in duration and will continue until the Sponsor elects to terminate the study. An overall schema of the study design is provided in Figure 1.

[figure not shown]
During Screening, patients who meet all eligibility criteria will be enrolled in the study, randomized in a 1:1:1 ratio to receive treatment with lower dose pitolisant, higher dose pitolisant, or matching placebo (20 patients per treatment group, ages 6 to 65 years) (Section 3.1.2). The lower and higher pitolisant doses, respectively in each age group, will be 8.9 mg and 17.8 mg for children ages 6 to <12 years, 13.35 mg and 26.7 mg for adolescents ages 12 to <18 years, and 17.8 mg and 35.6 mg for adults ages 18 to 65 years. In the Double-Blind Treatment Phase, patients will be titrated to their randomized stable dose of study drug during the Titration Period (Section 3.1.3). After completion of the Titration Period, patients will continue to take study drug at their randomized stable dose once daily in the morning upon wakening for an additional 8 weeks of blinded treatment (Stable Dose Period). The duration of the Double-Blind Treatment Phase will be 11 weeks.

Eligible patients who complete the Double-Blind Treatment Phase will be given the opportunity to participate in an optional OLE Phase.

In the OLE Phase, prior to implementation of Amendment 6, patients received a maximum target dose of pitolisant based on their age (17.8 mg for ages 6 to <12 years, 26.7 mg for ages 12 to <18 years, or 35.6 mg for ages 18 to 65 years; Section 3.1.4).

Safety, efficacy, and PK will be evaluated as detailed in Section 3.1.3 (Double-Blind Treatment Phase) and Section 3.1.4 (OLE Phase).

Figure 1: Overall Study Design

AE = adverse event; EOT = End of Treatment; F-Up = follow-up; OLE = Open Label Extension; PK = pharmacokinetics; TC = telephone call; V = Visit.

3.1.2. Screening and Baseline Visits

At the Screening Visit (Visit 1), after written informed consent/assent is provided, patients will complete screening assessments and will be provided with a sleep diary to measure daily sleep activity. Specific procedures and assessments for the Screening Visit (Visit 1) may be conducted remotely as detailed in Section 6.6.1.

The sleep diary is to be completed daily for 14 days (minimum of 7 days required for evaluation); patients will record (with the assistance of their caregiver if needed) the time they go to bed each evening and the time they wake up each morning (an example of the study diary, which includes a sleep diary section and a study drug dosing section, is provided in Appendix B). The patient will return the sleep diary to the site at the end of the 14-day period.

To be eligible for the study, patients must have a minimum of 7 evaluable nights from the 14 nights of sleep diary data. Using the patient-recorded times, a qualified study team member will calculate the evaluable hours and minutes the patient sleept per night. Using all evaluable nights, the mean subjective total sleep time (sTST) per night must be at least 8 hours for patients ages 6 to <12 years, at least 7 hours for patients 12 to <18 years, or at least 6 hours for patients ≥18 years.

At the Baseline Visit (Visit 2), patients who continue to meet all eligibility criteria based on their screening sleep diary will be randomized at a 1:1:1 ratio to receive once daily treatment with lower dose pitolisant, higher dose pitolisant, or matching placebo in the Double-Blind Treatment Phase (Section 3.1.3). Patients will not be stratified by age.

The stable doses of pitolisant (lower or higher) in the Double-Blind Treatment Phase are:

- 8.9 mg or 17.8 mg pitolisant in children ages 6 to <12 years
- 13.35 mg or 26.7 mg pitolisant in adolescents ages 12 to <18 years
- 17.8 mg or 35.6 mg pitolisant in adults ages 18 to 65 years

If the Screening Visit (Visit 1) was conducted remotely, refer to Section 6.6.1 for the procedures that will be conducted at the Baseline Visit (Visit 2).

After completion of all Baseline assessments eligible patients will be dispensed study drug at the Baseline Visit (Day -1) and will be instructed to take study drug once daily, beginning the following morning upon wakening (Day 1) in accordance with the schedule presented in Table 7. Patients will be instructed to record daily the number of tablets administered (and from which bottle) in the study drug dosing section of the study diary (with the assistance of their caregiver if needed). The study diary will be used in the Double-Blind Treatment Phase only (an example of the study diary is provided in Appendix B).

Study drug administration should begin in the morning on the day after the Baseline Visit; the first day of study drug administration is Day 1.

Patients who fail screening for any reason (e.g., sleep diary, laboratory test) may be rescreened once at the discretion of the Investigator.

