Open-Label Extension Phase

Long-term effectiveness of pitolisant as measured by ESS-CHAD (parent/caregiver version), CaGI-S for EDS, CGI-S for overall clinical status related to PWS, ABC-C, MERS-R-PWS, Cogstate Detection Test, Cogstate Identification Test, Cogstate One Back Test, ZBI-22, and HQ-CT in conjunction with the FSZQ will be assessed during the first year of participation (through Visit 9) in the OLE Phase of the study. After the first year, only ESS-CHAD (parent/caregiver version), CaGI-S, and CGI-S will continue to be assessed.

PHARMACOKINETIC AND PHARMACODYNAMIC ENDPOINTS

- C_{max} of pitolisant and its major metabolite, BP1.3484
- AUC_{last} after administration of pitolisant
- t_{max} of pitolisant
- Exposure-response relationship between pitolisant levels and change in efficacy measures

SAFETY ENDPOINTS

Safety will be assessed by monitoring the incidence of AEs and changes in clinical laboratory test results, vital signs, and 12-lead ECG results, along with additional safety assessments (suicidality, anxiety, and monitoring of seizures in patients with seizure disorder) from Baseline to Week 11 in the Double-Blind Treatment Phase and from Baseline to study completion in the OLE Phase.

STATISTICAL METHODS: All analyses will be performed using SAS[®] version 9.4 or higher, unless otherwise specified.

Primary Efficacy Analyses: Summary statistics (mean, standard deviation, median, minimum, maximum) for the primary efficacy endpoint of change in mean ESS-CHAD (parent/caregiver version) score from Baseline to Week 11 for pitolisant compared with placebo will be reported by treatment group and for the active groups combined. The change from Baseline will be analyzed in a mixed model repeated measures (MMRM) analysis. Fixed effects will be included for treatment, visit, treatment*visit interaction, Baseline value, and site. An unstructured covariance matrix will be utilized and if this fails to converge, then first-order autoregressive and compound symmetry will be attempted in that order; Kenward-Rogers degrees of freedom will be used. Least square (LS) means, standard errors, and the LS mean differences (each treatment vs placebo and the pooled active groups vs placebo) will be reported. All estimates will be generated from a single model, i.e., the pooled estimates will be created via model contrasts. The primary contrast of interest is the difference in the higher dose group versus placebo at Week 11.

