5.2.1. Study Drug Packaging and Labeling for the Double-Blind Treatment Phase

Study drug for the Double-Blind Treatment Phase will be packaged as individual patient-specific kits assigned by IRT. Each kit will consist of three boxes, one box for the Titration Period (titration sub-kit) and two boxes for the Stable Dose Period (stable dosing sub-kits; one box containing supplies for Days 22 to 49 and a second box containing supplies for Days 50 to 77).

For individual patients, the number of bottles and contents of the bottles will be based on the patient's randomized treatment assignment and age (Table 7).

The kit for the Double-Blind Treatment Phase for ADULTS will contain:

• Titration sub-kit:

- Two 10-count bottles, one labeled "A" and one labeled "B" for Week 1 (Days 1 to 7), containing pitolisant 4.45 mg or matching placebo tablets
- Two 20-count bottles, one labeled "A" and one labeled "B" for Week 2 (Days 8 to 14), containing pitolisant 4.45 mg or matching placebo tablets
- Two 10-count bottles, one labeled "A" and one labeled "B" for Week 3 (Days 15 to 21), containing pitolisant 17.8 mg or matching placebo tablets

• Stable dosing sub-kits:

- Two 30-count bottles, one labeled "A" and one labeled "B" for Weeks 4 to 7
 (Days 22 to 49), containing pitolisant 17.8 mg or matching placebo tablets
- Two 30-count bottles, one labeled "A" and one labeled "B" for Weeks 8 to 11
 (Days 50 to 77), containing pitolisant 17.8 mg or matching placebo tablets

The kit for the Double-Blind Treatment Phase for ADOLESCENTS will contain:

• Titration sub-kit:

- Two 10-count bottles, one labeled "A" and one labeled "B" for Week 1 (Days 1 to 7), containing pitolisant 4.45 mg or matching placebo tablets
- Two 20-count bottles, one labeled "A," one labeled "B," for Week 2 (Days 8 to 14), containing pitolisant 4.45 mg or matching placebo tablets
- Two 20-count bottles, one labeled "A," one labeled "B," and two 10-count bottles, one labeled "C," and one labeled "D" for Week 3 (Days 15 to 21), containing pitolisant 4.45 mg or matching placebo tablets

• Stable dosing sub-kits:

- Six 30-count bottles, two labeled "A," two labeled "B," one labeled "C," and one labeled "D" for Weeks 4 to 7 (Days 22 to 49), containing pitolisant 4.45 mg or matching placebo tablets
- Six 30-count bottles, two labeled "A," two labeled "B," one labeled "C," and one labeled "D" for Weeks 8 to 11 (Days 50 to 77), containing pitolisant 4.45 mg or matching placebo tablets

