9.4.2. Efficacy Analysis

9.4.2.1. Double-Blind Treatment Phase

9.4.2.1.1. Primary Efficacy Analysis

Summary statistics (mean, SD, median, minimum, maximum) for the primary efficacy endpoint of change in mean ESS-CHAD (parent/caregiver version) score from Baseline to Week 11 for pitolisant compared with placebo will be reported by treatment group and for the active groups combined. The change from Baseline will be analyzed in an MMRM analysis. Fixed effects will be included for treatment, Baseline value, visit, and treatment×visit interaction. An unstructured covariance matrix will be utilized, and if this fails to converge, then first-order autoregressive and compound symmetry will be attempted in that order; Kenward-Rogers degrees of freedom will be used. Least square (LS) means, standard errors, and the LS mean differences (each treatment vs placebo and the pooled active groups vs placebo) will be reported. All estimates will be generated from a single model, i.e., the pooled estimates will be created via model contrasts. The primary contrast of interest is the difference in the higher dose group versus placebo at Week 11.

Sensitivity analyses will utilize an approach identical to the primary analysis but on the dataset with imputed values. The 20 repeats will each be modeled independently, then combined using SAS Proc MI analyze and Rubin's approach (Rubin 1976).

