6.1 Changes from Protocol

- The Intent-to-Treat Population is renamed as modified Intent-to-Treat (mITT) Population, but the definition remains the same.
- The Pharmacokinetics (PK) Population was revised to include all patients who have at least one non-missing concentration for either analyte. This new definition of the PK Population means that all PK concentrations will be summarized and plotted even for patients with PK concentration available, but for which PK parameters cannot be determined.
- Additional details to resolve convergence issues for the mixed model repeated measures (MMRM) analysis with an unstructured covariance matrix was added.
- For the OLE Phase reporting, all patients will be analyzed under the same treatment group, i.e., patients will not be grouped based on their randomized treatment. During the OLE Phase, patients will undergo a 3-week titration to reach a target dose of 17.8 mg (ages 6 to <12 years), 26.7 mg (ages 12 to <18 years) or 35.6 mg (ages 18 to 65 years) and continue to received pitolisant at that dose (which corresponds to the high pitolisant dose for each age group as defined in the Double-Blind Treatment Phase) unless they were not titrated to the target dose and are receiving a lower dose based on clinical response and/or tolerability; therefore, the randomized treatment group will not influence the results of the OLE Phase.
- Remove the (pooled) site from all inferential models for consistency across analysis/endpoints. Most of the assessments are performed by the caregiver/patient so it is not expected for the site covariate to contribute to the model.

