8.3 Randomization

Eligible patients will be randomly assigned in a 1:1:1 ratio via an interactive voice/web response system (IXRS) to low dose pitolisant, high dose pitolisant, or matching placebo.

Enrolled patients will be allocated a unique patient number in a sequential order by trial site. Following randomization, Harmony Biosciences will provide all study drug in a packed and labeled kit, and the IXRS will identify the kit number to be dispensed to the patient at each relevant visit according to the treatment assigned in the randomization schedule.

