12.4.1.3.3 Analysis

A descriptive summary (mean, SD, median, minimum, maximum) of the mean ESS-CHAD (parent/caregiver version) score (absolute values and change from Baseline) will be reported by treatment group and for the active groups combined. Early Termination visits will be summarized under Visit 3, Visit 4 or Visit 5 (depending on which visit they are closest to, per section 9.2) regardless of the discontinuation reason.

Frequency count and percentage of the ESS-CHAD (parent/caregiver version) score category (state and percentage of the ESS-CHAD (parent/caregiver version) responder (improvement of points from Baseline or a score which is less or equal to will be tabulated by treatment group and active groups combined. Percentages will be based on the number of patients with non-missing ESS-CHAD (parent/caregiver version) at Baseline and at each post-baseline visit. Patients with a score at Baseline which is less or equals will not be included in the summary.

No explicit imputation will be performed for the primary analysis; however, the MMRM model will yield unbiased results under the assumption that data are missing at random.

The change from Baseline will be analyzed in an MMRM analysis. Fixed effects will be included for treatment, Baseline value, visit and a term for the interaction between treatment and visit. An unstructured covariance structure will be utilized; Kenward-Rogers degrees of freedom will be used.

In the case of convergence issues, the following steps will be implemented (in the order listed) until convergence is reached.

- 1. The Fisher scoring algorithm will be used to start the first iteration to obtain the initial values of the covariate parameters (via the SCORING option of the PROC MIXED statement).
- 2. The no-diagonal factor analytic structure (via the TYPE=FA0(T) option of the REPEATED statement, where T is the total number of time points), which effectively performs the Cholesky decomposition of the covariance matrix and is numerically more stable.
- 3. The successive univariate regression (Lu 2010) will be implemented.
- 4. Covariance matrix of ARH(1) (Heterogeneous auto-regressive 1), and CS (compound symmetry) with the sandwich variance estimator will be used in that order (for the sandwich variance estimator Kenward-Rogers degrees of freedom will be replaced by the EMPIRICAL option).

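### Neither the randomisation nor the primary MMRM accounts for age, so a chance age imbalance between high dose and placebo stays in the primary contrast; adding age group is a cheap improvement

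*Protocol*

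**What the plan says.** Protocol 3.1.2 randomises patients 1:1:1 at the Baseline Visit and adds: "Patients will not be stratified by age". SAP 8.3 repeats the ratio and names no stratification factor.

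Within each active arm the dose depends on age band; for the youngest band it is "8.9 mg or 17.8 mg pitolisant in children ages 6 to <12 years". Kits are assembled accordingly: the "contents of the bottles will be based on the patient's randomized treatment assignment and age" (Protocol 5.2.1). Age is therefore known when the kit is assigned. The minimum sleep duration for eligibility uses the same three bands.

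For the primary model, Protocol 9.4.2.1.1 has: "Fixed effects will be included for treatment, Baseline value, visit, and treatment×visit interaction". SAP 12.4.1.3.3 has: "Fixed effects will be included for treatment, Baseline value, visit and a term for the interaction between treatment and visit". The Protocol synopsis differs only by adding site: "Fixed effects will be included for treatment, visit, treatment*visit interaction, Baseline value, and site". SAP 6.1 settles that difference: "Remove the (pooled) site from all inferential models for consistency across analysis/endpoints". Protocol 9.1 lets the SAP govern where the two differ. No version contains age.

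The one planned sensitivity analysis of the primary endpoint (SAP 12.4.1.3.4) concerns missing data and uses the same terms. Age appears elsewhere only in the baseline tables (SAP 12.2.1), in the age-band subgroup analyses (SAP 12.4.1.6.5), and in the age-band displays of PK, exposure-response and safety.

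**The concern.** With 20 patients per arm and no stratification, the age mix of the high-dose and placebo arms will often differ noticeably. If change in ESS-CHAD varies with age beyond what the baseline score explains, the realised contrast carries part of that age difference, and any variance that age explains stays in the residual.

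The stated purpose of the trial is to give estimates precise enough to inform later studies, and the primary comparison rests on 20 against 20. A chance age mix that a single already-collected covariate could adjust for is worth removing. SAP 6.1 gives a reason for dropping site; neither document gives one for leaving age out.

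**Working it through.** **Inputs from the documents.** 20 patients per arm; ESS-CHAD SD of 5 to 6; design difference of 3.9 for pooled pitolisant against placebo at 80% power (Protocol 9.2); two-sided tests (SAP 12.4.1.1). Alpha is taken as 0.05, because the level is blacked out in the SAP and the protocol uses 95% intervals.

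**Assumptions, not in the documents.** The age mix, and the effect of age on change.

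**1. The plan's own figures.** For 40 against 20 at SD 5, power for 3.9 is 80.0% (noncentral t, 58 df). The half-width 1.96 × SD × √(1/20 + 1/40) is 2.68 at SD 5 and 3.22 at SD 6. These match the stated 80%, ±2.7 and ±3.2.

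**2. Half-width of the primary contrast.** For 20 against 20, t(0.975, 57 df) × SD × √(2/20) = 2.002 × 5 × 0.3162 = 3.17 at SD 5, and 3.80 at SD 6.

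**3. How often the arms differ in age.** Random permutations of 60 patients into 20/20/20, high dose against placebo:

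| Assumed mix (6 to <12 / 12 to <18 / 18+) | Some band differs by ≥4 | Some band differs by ≥5 | Adults differ by ≥4 | Adults differ by ≥5 |
|---|---|---|---|---|
| 20/20/20 | 47.6% | 29.3% | 24.6% | 13.3% |
| 24/18/18 | 47.0% | 28.6% | 23.1% | 12.3% |
| 15/15/30 | 44.7% | 26.6% | 27.1% | 15.7% |

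A separate run with another seed and equal bands gave 47.3%, 29.1%, 24.4% and 13.4%. With equal bands the difference in adult share has an SD of about 0.15, that is, 3 patients of 20; the median absolute difference is 2 patients.

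**4. Shift in the contrast.** Shift = (difference in adult share) × (adult-minus-younger gap in change, given baseline). With an assumed gap of 2 points:

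- median: 2/20 × 2 = 0.2 points
- root mean square: 0.15 × 2 = 0.3 points
- 4-patient imbalance: 4/20 × 2 = 0.4 points
- 5-patient imbalance: 5/20 × 2 = 0.5 points, reached or exceeded in about 13% of randomisations

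For gaps of 1 to 4 points, a 4-patient imbalance shifts the contrast by 0.2 to 0.8 points.

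**5. Precision with age group in the model (2 df).** Ratio of interval widths = √(1 − R²) × 1.018 × t(0.975, 54)/t(0.975, 56). R² is the share of residual variance explained by age. The factor 1.018 is the average penalty for estimating two age effects under unstratified allocation. The t ratio is 2.0049/2.0032 = 1.0008, so the two factors together give 1.019.

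| R² | Interval width against the planned model |
|---|---|
| 0 | 1.9% wider |
| 5% | 0.7% narrower |
| 10% | 3.3% narrower |
| 15% | 6.0% narrower |

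Break-even is 1 − 1/1.019² = 3.7%. A 2-point adult-versus-younger gap with equal bands explains 2² × (1/3) × (2/3) / 5² = 3.6% at SD 5. In that scenario precision is about unchanged, and the gain is only the removal of the conditional shift.

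**The case against.** The strongest reply has five parts.

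- **Validity.** A reader might infer that the primary contrast is biased or its test invalid. The documents do not support that. Randomisation keeps the unadjusted contrast unbiased on average and the type I error correct. This stands in full.

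- **No evidence of an age effect.** Using age for dosing and sleep thresholds does not show that it predicts 11-week change in ESS-CHAD, and any part of an age effect that acts through baseline sleepiness is already absorbed by the baseline covariate. This stands. Every shift and every R² above is an assumption.

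- **Dose by age is a different question.** A reader might infer that an age term would deal with the milligram dose varying by band. It would not. Placebo patients receive no drug, so this is a matter of effect modification, which the planned age-band subgroup analyses address. Protocol 1.3.1 also says that the paediatric doses were modelled from data suggesting higher exposure in children, so different milligrams need not mean different expected response.

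- **Partly covered already.** Age is tabulated by arm, and the subgroup analyses include ESS-CHAD, CaGI-S and CGI-S. An imbalance would be visible. These outputs still do not adjust the overall contrast.

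- **Deliberate parsimony.** This is a proof-of-concept study of 60 patients with openly stated non-stratification, no formal multiplicity control and no strict aim of statistical separation. A small model is defensible. That limits the importance of the point but does not argue against a 2-df adjustment or a sensitivity analysis.

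**Conclusion.** The point holds as a modest improvement. No version of the plan balances or adjusts for age in the high-dose versus placebo contrast. With equal bands assumed, some band differs by 4 or more of 20 patients in about 47% of randomisations; for adults alone the figure is about 25%. The consequence is conditional imbalance in the realised sample and possibly some lost precision.

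The likely size is small: a typical shift of 0.2 to 0.3 points if adults and younger patients differ by an assumed 2 points, against a half-width of about 3.2 at SD 5. Adjustment narrows the interval only if age explains more than about 4% of residual variance.

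**What to change.** If the double-blind data are still blinded, amend the SAP to add age group (6 to <12, 12 to <18, 18 or older) as a fixed effect in the primary and key secondary MMRMs and in the analysis model applied to the imputed data sets.

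That window may have closed. SAP 6.0 places its approval before unblinding, but Protocol 1.3.2, as revised by Amendment 6, describes the double-blind phase as completed and cites efficacy signals in the higher-dose group. If unblinding has occurred, leave the planned model as primary. Report the age-adjusted MMRM beside it as a clearly labelled post hoc sensitivity analysis, with age-band counts by arm.

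The cost is one covariate that is already collected, 2 degrees of freedom, and an interval about 2% wider if age explains nothing.
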